#### 8.1.4.2 Agent Usage

The agent usage will be compared between the two arms separately for each agent for the duration from induction to end of anesthesia. Usage of anesthetic agents will be normalized so that usage of different anesthetic agents can be pooled in analysis. It is intended to make claims on saving of anesthetic agent usage. The normalized anesthetic agent usage will be compared using t-test at two-sided alpha 0.05 between the Et Control Arm and Control Arm only if non-inferiority is concluded on primary endpoints; thus, no multiplicity adjustment is needed using the fixed sequence approach. The hypothesis to be tested on anesthetic agent usage is:

$$H_0: \mu_{\text{et}} - \mu_{\text{con}} = 0 \text{ vs } H_1: \mu_{\text{et}} - \mu_{\text{con}} \neq 0$$

where  $\mu_{\text{et}}$  is the average normalized anesthetic agent usage of the Et Control arm, and  $\mu_{\text{con}}$  is the average normalized anesthetic agent usage of the control arm.

Agent usage will also be analyzed for each agent.

Additional analysis on agent usage will be performed for the first 10 minutes after induction.

#### 8.1.4.3 User Setting Interaction

User setting interaction will be counted for the first 10 minutes following induction, and for the duration from induction to the end of anesthesia. The analysis may be performed for other time periods. Comparison between arms will be performed using non-parametric Wilcoxon rank sum method.

It is intended to make claims on user setting interaction for the duration from induction to the end of anesthesia, only when non-inferiority is concluded on primary endpoints and saving of anesthetic agent usage is concluded. So no multiplicity adjustment on alpha is needed. The hypothesis to be tested on user setting interaction for the duration from induction to the end of anesthesia is:

$$H_0: \mu_{\text{et}} = \mu_{\text{con}} \text{ vs } H_1: \mu_{\text{et}} \neq \mu_{\text{con}}$$

where  $\mu_{\text{et}}$  is the median of user setting interaction of the Et Control arm, and  $\mu_{\text{con}}$  is the median of user setting interaction of the control arm. Statistical significance will be declared if the Wilcoxon rank-sum test 2-sided p-value is less than 0.05.

#### 8.1.4.4 Time to Operating Room (OR) Discharge

Time to operating room (OR) discharge will be measured from end of surgery (*often defined as procedure end time, last stitch, or placement of last bandage*) to OR discharge (time of last breath, patient being disconnected from the anesthesia machine).

Hypothesis test on time to OR discharge will be performed only when non-inferiority is concluded on primary endpoints, saving on anesthetic agent usage and user setting

**Study Title:** Multi-site Anesthesia randomized controlled Study of End tidal control (Et Control) compared to conventional anesthesia Results (MASTER-Anesthesia Trial)  
**Study No:** 123.07-2015-GE5-0002

GE Healthcare

interactions are concluded. So no multiplicity adjustment on alpha is needed. The hypothesis to be tested on time to OR discharge is:

$$H_0: \mu_{\text{et}} = \mu_{\text{con}} \text{ VS } H_1: \mu_{\text{et}} \neq \mu_{\text{con}}$$

where  $\mu_{\text{et}}$  is the average time to OR discharge of the Et Control arm, and  $\mu_{\text{con}}$  is the average time to OR discharge of the control arm. Statistical significance will be declared if the student t-test 2-sided p-value is less than 0.05.

### 8.1.5 Et Control Accuracy

To assess the accuracy of Et Control in maintaining the target EtAA and EtO2 concentrations for each steady state, both mean absolute difference and mean percent difference between measured Et concentrations of AA and the setting values will be calculated, and the mean differences will be summarized for all steady states using descriptive statistics and 95% confidence intervals for each anesthetic agent and overall. The same accuracy analysis will be performed for EtO2. The mean differences will also be plotted against the setting values to assess consistency across the concentration range for each anesthetic agent. Percent of time duration in a steady state will also be assessed; when the percent difference exceeds 5%, 10%, and 15% of the setting values.

### 8.1.6 User Feedback

User survey and practice data on the effectiveness of training material and the ease to learn how to use Et Control will be summarized using descriptive statistics for the all subjects from each site.

### 8.1.7 Analysis of Adverse Events

Adverse events will be observed and recorded. Percent of subjects with AEs will be calculated, and comparisons between groups will be performed using Fisher exact test. Number of AEs and AE event rate will also be analyzed using non-parametric Wilcoxon method.

Analysis will be performed for a subset of adverse events of vital sign abnormalities including non-invasive blood pressure (NIBP), SpO2, and heart rate.

In addition, analysis of adverse events will be performed for each subset of patients defined by the pre-existing hypertension (*defined as a patient treated for hypertension*) status and ASA status.

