### 1.2.3 Human Studies – under U.S. FDA 21 CFR Part 812–Investigational Device Exemption (IDE)

A feasibility clinical study with human subjects was performed from 24/Feb/2014 to 30/Sep/2014 under the U.S. Food and Drug Administration (FDA) 21 Code of Federal Regulation (CFR) Part 812—Investigational Device Exemption (IDE) (*Study Title: Single Site, Randomized, Controlled Feasibility Study with and without Smartflow for Routine Anesthesia [Smartflow™ Feasibility], Study No. 123.01-2013-GE5-0001, FDA IDE No. G120300*). The purpose of this feasibility study was to collect and analyze safety and efficacy data on the investigational Et Control (formerly called as Smartflow) option to support the design of this pivotal clinical study. In this feasibility study, the Et Control option was used with the Aisys Anesthesia System, which was intended to provide general inhalation anesthesia and volume or pressure control ventilation support. There is no difference between Smartflow and Et Control (only a name change).

There were two arms in the study – Et Control (Smartflow) Arm (Aisys with Et Control) and the Control Arm (Aisys without Et Control). The study was conducted at University of Iowa Hospital and Clinics in Iowa City, Iowa, USA, and had a total of 28 evaluable subjects – 15 subjects in the Et Control Arm (6 females and 9 males) and 13 subjects in the Control Arm (9 females and 4 males). Results from the 28 evaluable subjects related to safety and efficacy were reported according to adverse events, Et Control performance, and comparison between the Et Control Arm and the Control Arm. Clinicians experiences in using the Et Control option were also reported.

There were no serious adverse events or deaths reported. Nine adverse events of hypotension were reported (6 were reported from the Et Control (Smartflow) Arm and 3 from the Control Arm). All events were anticipated and were considered hypotension. All events were determined by the clinician to likely not be related to the device or Et Control. All events were treated with medication, and resolved without sequelae.

Results showed evidence that Et Control (Smartflow) was able to successfully maintain and adjust settings in response to clinician selections, within a performance range equivalent to or potentially better than the Control Arm. Results also indicated that Et Control may reduce the duration of large deviations from the intended steady state settings.

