As described above, Et Control is an optional software/hardware feature that uses the same Aisys CS hardware (mixers, vaporization, breathing system and ventilator) and the same range of gas and vaporizer output to deliver the same dose levels of anesthetic gas concentrations to the subjects as selected by the clinician in the conventional Aisys CS fresh gas mode, and in accordance with the drug labeling. The Et Control option does not provide dosing guidance, or in any way alter the drug dosage as prescribed by the clinician. The Et Control option does not introduce any new types of hazards or harms to the subject.

With the mitigations in place, the use of Aisys CS with Et Control is expected to provide an equivalent safety/risk profile and Et Control does not introduce significant additional hazards to the subject.

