### 1.3.3 Conclusion

In summary, the Aisys CS with Et Control presents an equivalent risk profile to the currently marketed Aisys CS device, with several potential benefits in terms of workflow and human factors design, and additional safety mitigations. The risk/benefit assessment for this feature has resulted in the determination that the potential benefits outweigh the risks.

**Study Title:** Multi-site Anesthesia randomized controlled Study of End tidal control (Et Control) compared to conventional anesthesia Results (MASTER-Anesthesia Trial)  
**Study No:** 123.07-2015-GE5-0002

GE Healthcare

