### 3.3.2 Secondary Objective:

The secondary objectives are to:

- (1) gather additional functional and safety data in clinical use of the investigational Et Control option.
- (2) gather data on the amount of inhaled anesthetic agent and gas used in the Et Control Arm versus the Control Arm.

The hypothesis for the anesthetic agent usage is:

$$H_0: \mu_{et} - \mu_{con} = 0 \text{ vs } H_1: \mu_{et} - \mu_{con} \neq 0$$

where  $\mu_{et}$  is the average normalized anesthetic agent usage of the Et Control arm, and  $\mu_{con}$  is the average normalized anesthetic agent usage of the control arm.

- (3) obtain data on the number and frequency of user interactions with the Aisys CS user interface in the Et Control Arm versus the Control Arm.

The hypothesis for the user setting interaction for the duration from induction to the end of anesthesia is:

$$H_0: \mu_{et} = \mu_{con} \text{ vs } H_1: \mu_{et} \neq \mu_{con}$$

where  $\mu_{et}$  is the median of user setting interaction of the Et Control arm, and  $\mu_{con}$  is the median of user setting interaction of the control arm.

- (4) collect time to discharge from the operating room (OR), which is measured from the time of end of surgery (*often defined as procedure end time, last stitch, or placement of last bandage*) to time of last breath.

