### 8.1.2 Statistical Methods Overview

Data collected in this study will be presented using summary tables, data listings and graphs. Study endpoints and parameters will be summarized using descriptive statistics.

The descriptive statistics for continuous variables will include mean, standard deviation, median, Q1 and Q3, minimum, maximum, and sample size. Categorical variables will be described with counts, percentages, and sample size.

For comparison (between arms or against null values), categorical variables will be tested using appropriate contingency table analyses (exact or chi-square approximations), and continuous variables will be tested using Student's t-test or non-parametric methods, depending on variable distribution. P-values will be presented to three decimal places and p-values less than .001 will be presented as '<.001.'

**Study Title:** Multi-site Anesthesia randomized controlled Study of End tidal control (Et Control) compared to conventional anesthesia Results (MASTER-Anesthesia Trial)  
**Study No:** 123.07-2015-GES-0002

GE Healthcare

Subjects using different anesthetic agents will be pooled for analysis per the arm they are randomized. Separate analysis may be performed by anesthetic agent when pooling data across anesthetic agents is not appropriate.

No imputation will be performed for missing data unless specified otherwise.

A data extraction algorithm is used to identify periods of end tidal concentration measurement stability following setting changes (i.e. Steady States) during a case, as well as to measure response times, settling times, and overshoot amounts from these steady states in order to compare across arms. The extraction algorithm is not part of the statistical analysis, but provides the above-mentioned endpoints. (See Appendix 2 – Extraction algorithm for more information on the extraction algorithm.)

There will be two scenarios in defining a step change and steady state when performing the data extraction: 1) *using the data extraction algorithm to determine the desired end-tidal concentrations of anesthetic agent and oxygen for both arms* (See Appendix 2 – Extraction algorithm for more information on the extraction algorithm); 2) *using the clinicians recorded end tidal target values of anesthetic agent and oxygen for the Control arm, and the set target value for the Et Control arm.*

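### Adverse events are compared between arms by significance tests alone, with no risk difference or confidence interval, so a non-significant result would not show how large an excess has been excluded

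*Combined protocol and SAP*

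**What the plan says.** Section 8.1.7 sets out the adverse event comparison in two sentences. For the percentage of subjects affected, "comparisons between groups will be performed using Fisher exact test"; beyond that, "Number of AEs and AE event rate will also be analyzed using non-parametric Wilcoxon method". The analysis is repeated for vital-sign events (blood pressure, SpO2, heart rate) and within subsets by pre-existing hypertension and ASA status. The section gives no effect measure, interval, significance level or margin. The general rules in 8.1.2 do not fill the gap: categorical variables are described by counts and percentages and then tested by contingency-table methods.

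Elsewhere the plan does use intervals. Section 8.1.3 judges the primary endpoints by a two-sided 95% interval for the difference, and 8.1.5 reports device accuracy with 95% intervals.

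On risk, section 1.3.1 states that the device with Et Control "is expected to provide an equivalent safety/risk profile", and section 1.3.3 concludes that it "presents an equivalent risk profile to the currently marketed" device. The trial's own safety objective in 3.3.2 is more modest: to "gather additional functional and safety data in clinical use of the investigational Et Control option". Section 8.4 rests pass or fail on EtAA and EtO2 alone.

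**The concern.** A test of no difference answers whether an excess has been demonstrated. It does not say how large an excess is still compatible with the data. If the favourable safety result is a large p-value, a reader who has met the equivalent-risk language in section 1.3 may take it as confirmation. That is a step the test cannot support at this sample size. The protocol classes the option as a significant risk device (2.3) and intends the trial to support a US marketing application (3.1), so the size of the excess excluded is something a reader will want to know. The plan as written does not commit to stating it.

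**Working it through.** **Inputs.** About 124 subjects per arm, 1:1 (5.1). Safety population: all randomized subjects anesthetized with either device (8.1.2.1), so close to 124 per arm. If the whole 15% drop-out allowance were lost, 124 × 0.85 ≈ 105. Section 8.1.7 gives no alpha, so two-sided 0.05 is assumed. No AE rate is given for this trial, so control rates from 1% to 40% are assumed.

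**Step 1: the plan's own sample size.** For non-inferiority of means, n = 2·SD²·(1.96 + 1.645)² / (difference + margin)².
- EtAA: 2·16²·12.996 / (3 + 5)² = 103.97, so 104. The t-based solution is 105, and 105 / 0.85 = 123.5, so 124.
- EtO2: 2·19²·12.996 / (8 + 5)² = 55.5, so 56. The t-based solution is 57, and 57 / 0.85 = 67.1, so 68.

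Both match Table 8-1. The number was set by performance; safety played no part in it.

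**Step 2: power of Fisher's test.** Exact power is the sum of Bin(x; n, p1)·Bin(y; n, p2) over all (x, y) with two-sided Fisher p below 0.05. Results are for 124 per arm, with 105 per arm in brackets:

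| Control rate (assumed) | +5 points | +10 points | +15 points | Excess with 50% power |
|---|---|---|---|---|
| 10% | 17% (14%) | 53% (46%) | 85% (78%) | 9.6 (10.6) points |
| 23% | 12% (10%) | 36% (31%) | 68% (60%) | 12.1 (13.2) points |
| 40% | 10% (9%) | 30% (25%) | 61% (52%) | 13.3 (14.7) points |

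For rare events, 1% against 4%, power is 16% (11%). The 50% point at a 1% control rate is 5.4 (6.2) points. Power is lower again within the hypertension and ASA subsets, which are smaller.

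**Step 3: an excess of the feasibility size.** Section 1.2.3 reports: "Nine adverse events of hypotension were reported (6 were reported from the Et Control (Smartflow) Arm and 3 from the Control Arm"). With 15 and 13 evaluable subjects, and assuming one event per subject, this is 6/15 = 40% against 3/13 = 23%, a difference of 16.9 points. Power at those rates is 79% at 124 per arm and 71% at 105.

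**Step 4: what an interval would add.** The Newcombe limits for d = p1 − p2 use the Wilson limits (l, u) of each arm: upper = d + √[(u1 − p1)² + (p2 − l2)²].
- Equal arms, 29/124 each: p = 0.234, Wilson limits 0.168 to 0.316. Upper limit = √(0.082² + 0.066²) = 0.105, so identical observed rates still leave +10.5 points open. Other equal splits give +5.9 (6/124 each), +7.6 (12/124 each) and +12.0 (50/124 each).
- 44/124 against 29/124: d = +12.1 points, Fisher p = 0.051, so not significant. The 95% interval is +0.75 to +23.0 points. The interval just excludes zero while the test does not reach 0.05, because Fisher's test is conservative.

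In the feasibility data, 6/15 against 3/13 gives Fisher p = 0.43 and a 95% interval of −16.9 to +45.4 points.

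**The case against.** The strongest reply is that the trial makes no safety-equivalence claim. The equivalence wording belongs to the device risk analysis, which argues from hazards, failure modes and mitigations. The trial's objective is to gather safety data, the endpoint is to count and compare events (3.4.2), and no section says that a non-significant Fisher test will be read as equal risk. This stands. A reader might infer that the trial sets out to prove equivalent safety, but the documents do not support that. What remains is narrower: if the aim is to gather and compare, estimation serves it better than a test alone.

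A reader might also infer that any real excess would most likely go unreported. Step 3 contradicts this. Above about 10 to 13 points at control rates of 10-40%, detection is more likely than a miss.

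Nor does the feasibility study establish a harm signal. It reports events rather than affected subjects, and hypotension only. The documents do not show that it used the thresholds now in section 10.2. All events were judged likely not device-related and resolved, and none was serious. The interval in Step 4 is very wide on both sides of zero.

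Finally, the percentages and denominators will be tabulated, so anyone could calculate an unadjusted interval afterwards. That is correct, so the gap lies in the prespecified analysis and not in the data. The DSMB, the enrollment pause at three Et Control subjects with an SAE or UADE (11.2), the vasoactive drug comparison (8.1.8) and the summaries of concentrations around each event (8.1.9) are real safeguards. None of them bounds the between-arm difference in adverse events.

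**Conclusion.** The point holds as a weakness in how the safety comparison is specified. Section 8.1.7 plans tests without estimates, and at 124 per arm a non-significant Fisher result is the more likely outcome for a true 5-point excess at every control rate from 10% to 40% (power 10-17%). For a 10-point excess, power runs from about an even chance at a 10% control rate (53%) down to 30% at 40%. Such a result would leave the excluded harm unstated and could not be cited for the equivalent-risk statement in section 1.3. The point does not extend to large excesses, to any trial claim of safety equivalence, or to a demonstrated hypotension signal.

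The figures rest on two-sided 0.05, near-complete inclusion in the safety population, and assumed control rates. The 23% rate comes from 3 events in 13 subjects under a one-event-per-subject assumption, and serves as one value in a range. The primary conclusion of the trial is not affected.

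**What to change.** In 8.1.7, for any adverse event and for each vital-sign subset, report the risk difference (Et Control minus Control) with a two-sided 95% interval:
- unadjusted, by Newcombe or Miettinen-Nurminen;
- Mantel-Haenszel stratified by hypertension and ASA status, both already randomization factors.

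Investigator is also a randomization factor but is likely too sparse to add. At the minimum of 10 cases per investigator there could be up to 24 investigators (248 / 10 = 24.8), and 24 × 2 × 3 = 144 strata would average under two subjects each.

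For event counts, give a rate ratio with a 95% interval and name the model in advance, for example negative binomial.

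Describe safety by the estimate and its interval, and state that non-significance will not be read as equal risk. Keep the Fisher and Wilcoxon p-values as supplementary, since test and interval can disagree near the boundary. No safety margin is needed, because the trial has no safety hypothesis.

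The cost is some extra programming and table work, with no new data, visits or subjects. The drawback for the sponsor is that the interval may show openly that a sizeable excess cannot be excluded.

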### 8.1.8 Analysis of Vasoactive Medication Use

When vasoactive medication is used during the anesthesia procedure, the medication name, reason for use, amount used, duration of use will be recorded. Usage of vasoactive medication will be analyzed for the Et Control and the Control Arms in terms of types of vasoactive medication used, reason for use, number of subjects and total dose. The

**Study Title:** Multi-site Anesthesia randomized controlled Study of End tidal control (Et Control) compared to conventional anesthesia Results (MASTER-Anesthesia Trial)  
**Study No:** 123.07-2015-GE5-0002

GE Healthcare

vasoactive medication use will be analyzed by ASA status and by preexisting hypertension status. Comparison for categorical variables will be performed using Fisher exact test and comparison for numerical variables will be performed using Wilcoxon rank-sum method.

### 8.1.9 Other Analysis

Delivered EtAA and EtO2 concentrations will be summarized by anesthetic agent and overall for both arms to demonstrate the comparability in anesthesia practice.

Delivered EtAA and EtO2 concentrations and their deviations to set values for the duration of +/- 10 minutes of an AE will be summarized for both arms.

Oxygen (O2) usage from induction to the end of surgery will be summarized and compared between the two study arms using t-test.

Post-anesthesia discharge time will be summarized and compared between the two study arms using t-test. Post- anesthesia discharge time is defined as OR discharge (patient disconnected from the anesthesia machine) to discharge time from the PACU (*defined as the time patient meets criteria to discharge from PACU*).

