## 5. STUDY SUBJECTS

### 5.1 Number of Subjects

A total of 248 Subjects will be enrolled in the study, with approximately 124 subjects enrolled in each arm: Et Control Arm and Control Arm. A minimum of 15 subject cases is the target enrollment for each of the 3 anesthesia agents (Desflurane, Sevoflurane, and Isoflurane) per arm (*only one inhalation anesthetic agent may be used for each enrolled subject in the study arm*).

The study will be conducted at 4 hospitals (investigational sites) located within the United States. Each investigational site is to enroll a minimum of 30 to a maximum of 80 subjects with approximately 1:1 ratio for subject in the Et Control Arm and Control Arm.

Each Investigator will be performing a minimum of five (5) cases for each arm (Et Control and Control). In situations where the Investigator is unable to complete a minimum of 5 cases in each arm, a Sponsor exception may be obtained. Subjects will be randomized to the Et Control Arm or the Control Arm, and randomization will be stratified based on Investigator, subject's pre-existing hypertension status, and subject's ASA status.

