## 8. DATA ANALYSIS AND STATISTICS

### 8.1 Statistical Analysis Methods

#### 8.1.1 Sample Size Determination

This study is intended to demonstrate that Et Control is non-inferior to the control device in maintaining end tidal anesthetic agent (EtAA) and end tidal oxygen (EtO2) concentrations.

The primary efficacy endpoint is the weighted average per subject of percent duration of EtAA and EtO2 concentrations maintained within the acceptable range for a subject. The acceptable range is specific for each steady state. For EtAA, the acceptable range is defined as +/- the larger of 5% of the steady state concentration or 0.1% v/v for Iso, 0.2% v/v for Sev, 0.6% v/v for Des; and for EtO2, it is +/- 5% v/v. The duration of each steady state will be used as the weight when calculating the weighted average. For EtAA,

$$\text{PercentDuration} = \frac{\sum_j \sum_i t_{ij} I_{ij}}{\sum_j T_j} \times 100\% \quad \text{where } t_{ij} \text{ is the } i^{\text{th}} \text{ duration of EtAA concentration}$$

maintained within the acceptable limit during the  $j^{\text{th}}$  steady state, and  $T_j$  is the total duration of the  $j^{\text{th}}$  steady state.  $I_{ij}$  is an indicator for whether EtAA is maintained within the acceptable limit of  $i^{\text{th}}$  duration in  $j^{\text{th}}$  steady state, which is

$$I = \begin{cases} 1 & \begin{array}{l} \text{if Desflurane and } \Delta\text{EtAA} \leq \max(0.6\%, 5\%X \text{ steady state EtAA}) \\ \text{if Sevoflurane and } \Delta\text{EtAA} \leq \max(0.2\%, 5\%X \text{ steady state EtAA}) \\ \text{if Isoflurane and } \Delta\text{EtAA} \leq \max(0.1\%, 5\%X \text{ steady state EtAA}) \end{array} \\ 0 & \text{otherwise} \end{cases}$$

$\Delta\text{EtAA}$  is the absolute difference between measured EtAA concentrations and steady state EtAA concentration.

Similar definition is used for EtO2 except that acceptable limit is set as 5% v/v.

From the results of the feasibility study, the average percent duration of EtAA and EtO2 concentrations that exceeded the defined acceptable range for the Control Arm was about 13% and about 18%, respectively. In this study, the non-inferiority margin is set at 5% for both EtAA and EtO2, which is about 1/3 of the performance of the Control Arm, i.e., Et Control will be considered non-inferior to the control device if its performance is no worse than that of the control device by more than 5%.

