So the hypotheses on the primary endpoints are:

$$H_0: \mu_{\text{et}} - \mu_{\text{con}} < -5\% \text{ vs } H_1: \mu_{\text{et}} - \mu_{\text{con}} \geq -5\%$$

**Study Title:** Multi-site Anesthesia randomized controlled Study of End tidal control (Et Control) compared to conventional anesthesia Results (MASTER-Anesthesia Trial)  
**Study No:** 123.07-2015-GE5-0002

GE Healthcare

for both EtAA and EtO2, where  $\mu_{et}$  is the percent duration of Et Control with EtAA and EtO2 maintained within the acceptable range, and  $\mu_{con}$  is the percent duration of control device with EtAA and EtO2 maintained within the acceptable range.

Both null hypotheses have to be rejected for EtAA and EtO2 to conclude non-inferiority. So the alpha is set at 0.025 one-sided with no need for multiplicity adjustment, but the power for each hypothesis is set at 0.95 to have an overall power of 0.9 for the study. And the larger sample size calculated for EtAA and EtO2 will be the size of the study.

The results from the feasibility study on the weighted average of percent duration with EtAA and EtO2 maintained within the acceptable range is listed below. The difference between Et Control and control device is assumed to be 50% less than what was observed, and the larger standard deviation observed is used in sample size calculation using the 2-sample t-test method.

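### Section 8.1.9 sets out to show comparable delivered EtAA and EtO2 from arm summaries alone; it should report the between-arm difference with a confidence interval, on a MAC scale when EtAA is pooled

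*Combined protocol and SAP*

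**What the plan says.** Under Other Analysis (8.1.9), "Delivered EtAA and EtO 2 concentrations will be summarized by anesthetic agent and overall for both arms to demonstrate the comparability in anesthesia practice". No between-arm difference, interval, limit or decision rule is attached. The same section treats oxygen consumption differently: for that variable, "usage from induction to the end of surgery will be summarized and compared between the two study arms using t-test", and post-anesthesia discharge time is handled in the same way. The general rule in 8.1.2 for between-arm comparisons is that "continuous variables will be tested using Student's t-test or non-parametric methods, depending on variable distribution".

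Three other places bear on the point:
- Section 8.1.4.2: "It is intended to make claims on saving of anesthetic agent usage". The comparison is a two-sided t-test on normalized usage. The only stated reason for normalizing is to let different agents be pooled, and no formula is given.
- Section 5.1: "A minimum of 15 subject cases is the target enrollment for each of the 3 anesthesia agents", in each arm. Agent is not among the stratification factors (investigator, hypertension status, ASA status).
- Section 8.1.1: "the non-inferiority margin is set at 5% for both EtAA and EtO 2". This margin is in percentage points of time within limits. It does not apply to the concentration delivered.

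**The concern.** Showing that two arms were run alike is an equivalence-type aim, and side-by-side means and SDs cannot meet it. They leave the reader to judge by eye how large a difference is still compatible with the data.

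No other planned analysis addresses the level at which the arms were run. In scenario 1 the primary endpoint measures deviation from the subject's own averaged steady state (Appendix 2, step 4). In scenario 2 it measures deviation from the recorded or set target (3.4.1). A shift between arms in the level chosen enters neither. Question 5 of the user survey (6.3.5) asks about equal targets, but it is a yes/no self-report by an unblinded clinician.

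What is at stake is how the agent-usage result is read. If Et Control cases ran at a lower EtAA, usage would fall partly for that reason. A reader would need the EtAA difference and its precision to see how much of the saving that could explain.

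**Working it through.** **1. Numbers available.** The plan gives no figure for the precision of this comparison, so I first confirm the sample size. From Table 8-1 for EtAA: SD 16, expected means 90 and 87, margin 5, one-sided alpha 0.025, power 0.95. The distance from the margin is 5 + 3 = 8. The noncentral-t calculation gives 105 per arm, and 105 / 0.85 = 123.5, rounded up to 124. This reproduces the plan's 124 per arm (248 in total). Pooled precision is therefore shown at 105 (after 15% dropout) and at 124. For one agent I use the target minimum of 15 and, for orientation, an even spread: 248 / 6 agent-by-arm cells = about 41.

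**2. Scale of the overall EtAA summary.** The footnote at section 2.1.3 gives 1 MAC as 6.0 (desflurane), 2.1 (sevoflurane) and 1.15 %v/v (isoflurane). Suppose every subject in both arms is held at exactly 1 MAC. Each subject who has desflurane instead of isoflurane then moves an arm's overall %v/v mean by (6.0 − 1.15) / 124 = 0.039. Three such subjects move it by 0.117, more than the 0.1 %v/v isoflurane limit in 3.4.1, with no difference in MAC dose. On a %v/v scale the overall summary partly reflects agent mix.

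The plan's EtAA limits on the MAC scale, for reference only, are 0.6 / 6.0 = 0.100, 0.2 / 2.1 = 0.095 and 0.1 / 1.15 = 0.087 MAC.

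**3. Precision of the between-arm difference.** The 95% half-width is t(0.975; 2n − 2) × SD × √(2/n). The between-subject SD is not in the documents, so it is assumed. For n = 15 the factor is 2.048 × 0.365 = 0.748; for n = 124 it is 1.970 × 0.127 = 0.250.

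| n per arm | SD 0.15 MAC | SD 0.20 MAC | SD 0.30 MAC |
|---|---|---|---|
| 15 | 0.112 | 0.150 | 0.224 |
| 41 | 0.066 | 0.088 | 0.132 |
| 105 | 0.041 | 0.054 | 0.082 |
| 124 | 0.038 | 0.050 | 0.075 |

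For EtO2 at an assumed SD of 5 / 10 / 15 / 20 %v/v, the half-width is 3.74 / 7.48 / 11.22 / 14.96 %v/v at 15 per arm and 1.25 / 2.50 / 3.75 / 5.00 %v/v at 124 per arm.

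At the agent minimum and these EtAA SDs, data with identical arm means would still be compatible with a shift above 0.10 MAC. When pooled they would not.

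**4. Link to usage (illustration).** Assume usage is proportional to EtAA at equal flow. A shift of 0.087 to 0.10 MAC around 1 MAC then lowers usage by about 9% to 10%. With 105 per arm, the two-sided 0.05 t-test would find a 10% reduction significant with probability 95% / 67% / 44% / 30% at an assumed usage CV of 20% / 30% / 40% / 50%. A difference in level of that size could by itself produce a significant usage result.

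**The case against.** The strongest reply is that nothing rests on this sentence. It sits under Other Analysis and is not an objective, an endpoint, part of the fixed sequence in 8.1.2 or the pass criterion in 8.4. Section 8.1.2 prescribes means, SDs and sample sizes, so a shift would be visible and a reader could compute an interval. Intended concentrations are also captured in both arms, as recorded targets for Control and set targets for Et Control. All of this stands and limits the weight of the point. It does not make a summary sufficient for the stated purpose, and no between-arm comparison of those targets is planned.

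A reader might go further in three ways that the documents do not support.
- **That a non-significant t-test will be taken as proof of comparability.** Section 8.1.9 prescribes no test for delivered concentrations, in contrast to its lines on oxygen usage and discharge time. Even if a t-test were applied, at SDs of 0.15 to 0.30 MAC a 0.10 MAC shift would be missed in 58% to 86% of trials at 15 per arm, but in only 0.1% to 26% when pooled at 124 per arm (0.2% to 33% at 105).
- **That the agent-saving result would be invalid.** Usage is compared as randomized. If allocation changes the concentrations chosen, lower usage is still a valid effect of allocation, and 8.1.4.2 does not claim a saving at equal EtAA.
- **That the plan's 0.6 / 0.2 / 0.1 and 5 %v/v limits are the natural acceptance rule.** They classify deviations within a subject, and for EtAA they are floors. With no true difference, a pooled 95% interval at 124 per arm would lie inside ±0.10 MAC only 76% of the time at SD 0.25 and 49% at SD 0.30.

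**Conclusion.** The point holds as one of analysis and wording. Section 8.1.9 states an aim that its summaries cannot meet, and its overall EtAA summary needs a common scale. The usage comparison is not stated to account for delivered EtAA. The weakness is largest within an agent near the minimum of 15 per arm (half-width about 0.11 to 0.22 MAC) and modest when pooled (about 0.04 to 0.08 MAC at 105 to 124 per arm).

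These widths rest on an assumed SD of 0.15 to 0.30 MAC, and pooling rests on the single-age MAC values in the footnote. The usage illustration also needs proportionality at equal flow and an assumed CV. The primary non-inferiority conclusion, the 248 subjects and the order of testing are unaffected.

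**What to change.** In section 8.1.9:
1. Compute each subject's time-weighted mean delivered EtAA, in %v/v within agent and in multiples of the footnote MAC values for pooling, and each subject's mean EtO2.
2. Report the Et Control minus Control difference with its 95% confidence interval, pooled and by agent. Label the per-agent intervals descriptive.
3. Present these differences beside the agent-usage result of 8.1.4.2.
4. Reword the stated purpose as describing the between-arm difference. If the sponsor wants to keep a claim of comparability, it should pre-specify and justify its own between-arm limit. The existing within-subject limits may be drawn as reference lines without serving as the acceptance rule.

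Breath-by-breath EtAA and EtO2 are already logged (6.3.2), so the cost is SAP wording and one table, with no added subjects or procedures. The small downside is a weaker comparability statement where an interval is wide, mainly within a single agent.
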